3.1 Inclusion Criteria

- 3.1.1. HIV infected; must be documented or presumed at entry. (See section 8.1.2.2.)
- 3.1.2. Symptomatic anemia (as defined by the treating physician) with planned RBC product for a transfusion that can wait 4 hours.
- 3.1.3. The reason for the initial transfusion event must be non-surgical (e.g., no surgery requiring general anesthesia in the prior 2 weeks and the current transfusion is not in preparation for an upcoming surgery).
- 3.1.4. Age ≥ 14 years.
- 3.1.5. Patients must have evidence of current or past CMV infection. Patients must have documented CMV end organ disease or have a positive CMV culture, antigen assay, antibody assay or diagnostic histology prior to enrollment.
- 3.1.6. Karnofsky score ≥ 40 (See Appendix II).
- 3.1.7. Expected survival > 1 month.
- 3.1.8. Expected to be available for follow-up for at least one month.
- 3.1.9. Informed consent obtained from patient or guardian.

3.2 Exclusion Criteria

- 3.2.1. Prior transfusion history including red blood cells, whole blood, platelets or other blood components or transplantation of tissues/organs with potential for viral transmission (Factor concentrates, cryoprecipitate, plasma).
- 3.2.2. Intravenous immunoglobulin within 6 weeks prior to entry.
- 3.2.3. Initiation of a new antiretroviral therapy, systemic immunomodulator (e.g., IL-2, Interferons) or GM-CSF within 2 weeks prior to entry.
- 3.2.4. Thrombotic thrombocytopenic purpura (TTP).
- 3.2.5. Renal failure requiring any form of dialysis.
- 3.2.6. Patients who have medical conditions which, in the opinion of the study staff, will interfere with study compliance.
- 3.2.7. Patients requesting directed donations.
- 3.2.8. Patient's physician objects to in laboratory leukocyte filtration.

Section 4 -- Registration & Randomization

4.1. Treatment Groups

Patients will be allocated randomly to one of two treatment groups: Leukocyte Reduced Red Blood Cells or Non-Leukoreduced Red Blood Cells . Except as specified in section 5.3, all RBC transfusions required while on-study (see section 7.2 for definition of on-study) should be according to the randomized treatment group.

4.2. Stratification Factors

Randomization will be stratified by CD4 or total lymphocyte count and by CMV disease. A dynamic balancing method⁵⁷ will also be used to ensure treatment balance within each institution.

4.2.1. CD4 or Total Lymphocyte Count. For purposes of this stratification factor, CD4 count history should be based on medical record or physician report. If these are not available, CD4 count may be based on patient self-report if the clinical coordinator judges it to be reliable. The two levels of this stratification factor are:

4.2.1.1. CD4 count $<50/\mu\text{L}$ at any time in the past. In cases where CD4 count was never known to be $<50/\mu\text{L}$ and there is no history of $\text{CD4} \geq 50$ within the past month, total lymphocyte count $< 1000/\mu\text{L}$ within one week prior to study entry.

4.2.1.2. Not meeting criteria 4.2.1.1 (i.e., available documentation or reports suggest $\text{CD4} \geq 50/\mu\text{L}$, within the past month, or in absence of this information, total lymphocyte count $\geq 1000/\mu\text{L}$ within one week prior to study entry).

4.2.2. CMV Disease. (All patients must have evidence of current or past CMV infection.) The two levels of this stratification factor are:

4.2.2.1. Current or previous diagnosis of CMV end organ disease (excluding viremia alone; see sections 7.3 and 7.4).

4.2.2.2. No current or previous diagnosis of CMV end organ disease.

4.3. Patients are registered and randomized with the following procedure.

4.3.1. Verify eligibility criteria (see sections 3 and 8.1), ascertain stratification factors, (sections 4.2 and 8.1.3) and obtain signed informed consent. Clinic Randomization Form is completed. Eligible patients are assigned the next sequential patient ID number.

4.3.2. Call the coordinating center (NERI) at [contact] from a touch tone phone. The caller will be asked questions to ascertain clinical site, patient ID number, eligibility, and stratification factors. The caller will receive a coded treatment assignment in the form of a five digit number.

- 4.3.3. If phone is busy, wait five minutes and try again. If after three tries the phone is still busy, or if phone call does not go through, open the next sequential sealed envelope. The envelope will contain a coded treatment assignment in the form of a five digit number. Call the VATS Data Manager at [contact], [name] to report the problem. Go to step 4.3.4.
- 4.3.4. Each site will have a set of labels with potential VATS ID numbers for that site. Two labels with the assigned VATS patient ID should be used. One goes on the Clinic Randomization Form and other goes on the Blood Bank Randomization Form. The coded treatment assignment should be written on the Blood Bank Randomization Form.
- 4.3.5. The original Blood Bank Randomization Form is taken to the blood bank. (A copy should go to the study file). The blood bank will have the key to determine to which treatment group the patient has been assigned.
- 4.3.6. Blood bank personnel will circle the assigned treatment assignment on the Blood Bank Randomization Form and prepare the blood units (See Section 5.1.) **IT IS IMPORTANT TO KEEP THE TREATMENT ASSIGNMENT BLINDED TO OTHER STUDY STAFF AND TO THE PATIENT.** The blood bank will keep a copy of the Blood Bank Randomization Form (again, not available to other staff) and refer to it in the event of any subsequent transfusions. (Ordinarily, all subsequent transfusions will be prepared in the same way as the original transfusion. See section 5.3).
- 4.3.7. The Blood Bank will mail the original Blood Bank Randomization Form to NERI within 24 hours, using the envelope provided.
- 4.3.8. NERI will send a confirmation of registration to the clinical coordinator.

Section 5 -- Product Preparation, Administration & Blinding

5.1 Study Components

For the purposes of this protocol, the following terms will be used interchangeably and all refer to a blood component rendered leukocyte reduced as specified: leukocyte reduced, leukoreduced, leukodepleted, or leukocyte filtered.

- 5.1.1. Red cell leukoreduction will occur prestorage, within 72 hours of collection.
- 5.1.2. Leukoreduction filter type will not be specified but will be recorded. Study sites will obtain from their suppliers blood filtered to contain no more than 5×10^6 leukocytes. Quality assurance data will be obtained from suppliers.
- 5.1.3. No units will be more than 14 days in age. Within the inventory of 14 day old or less units, the oldest unit will be chosen for issue. If no units 14 days or less are in the inventory, the blood bank should make every effort to obtain a unit(s) of appropriate age. The age of all units will be recorded. Following transfusion of every 20 units at a site, NERI will evaluate for bias of age between the two arms.
- 5.1.4. All platelet components will be leukocyte reduced unless emergent transfusion is indicated in which case every effort will be made to provide a leukocyte depleted component. Apheresis platelets are preferred, however the freshest available platelet components are to be issued.
- 5.1.5. A whole blood segment will be obtained from the original collection bag. A second sample of donor blood will also be obtained from the study bag of packed red blood cells at the time of issue. For platelet transfusions, a single sample at the time of issue will be retained (from each apheresis unit or pool). (See Laboratory Procedures section of the VATS Study Manual for storage and shipment information.)
- 5.1.6. Components will not be required to be CMV screened prospectively.
- 5.1.7. In compliance with AABB standards and federal regulations, all red blood cells will be ABO group compatible. Within these standards and for the purpose of this study all red blood cell units issued will be either group O or A. Red blood cell components will not be irradiated, except as per section 5.1.10.
- 5.1.8. Leukocyte filtration of all blood components will be performed at the blood center or transfusion service unless emergency transfusion requires bedside filtration per section 5.1.4.
- 5.1.9. The weight of each component will be recorded by transfusion service staff at the time of issue.
- 5.1.10. Irradiated study components will be allowed if, after enrollment, a patient develops a condition (e.g., lymphoma) requiring irradiated components. The patient should continue to receive blinded study components, either leukoreduced or non-leukoreduced, except that irradiation of components will not be prohibited.

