Transfusion-associated graft-versus-host disease (TA-GvHD) occurs in immunocompromised persons who are transfused with blood containing viable allogeneic lymphocytes, i.e. non-irradiated blood stored at 4°C less than 2 weeks.⁴⁰⁻⁴² TA-GvHD has been described in individuals with bone marrow transplants, congenital immune deficiency states, and in some cancer patients. Recently TA-GvHD has been reported in immunocompetent individuals who receive blood from family members with closely related HLA type, or from donors who, by chance, share an HLA haplotype with the recipient.^{41,42} Data also suggest that donor lymphocytes proliferate transiently in immunocompetent recipients, apparently in an abortive GvHD reaction.²³ Adequate gamma-irradiation of blood products eliminates this risk. The American Association of Blood Banks recommends irradiation of all blood transfused to individuals with these underlying diseases, as well as to persons receiving blood from closely related persons. Surprisingly, TA-GvHD has not been reported in AIDS patients.^{43,44} This may be because cases of TA-GvHD in AIDS patients go unrecognized because many of the clinical manifestations of GvHD regularly occur in late stage HIV-1 infection. Alternative explanations for the absence of TA-GvHD in AIDS patients include rapid infection and destruction of proliferating alloreactive donor lymphocytes by HIV,⁴³ or failure of the HIV-infected patient's immune system to contribute effector cells to the GvHD immunopathological process.^{44,45} No studies have been reported to date that directly examined persistence of donor leukocytes in HIV-infected transfusion recipients.

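### Section 5.1.10 lifts the ban on irradiated red cells only for a need that arises after enrollment, and no eligibility criterion names a patient who already has that need at screening

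*Protocol*

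**What the plan says.** All references are to the Protocol.

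- **The ban.** Section 5.1.7: "Red blood cell components will not be irradiated, except as per section 5.1.10".
- **The only exception.** Section 5.1.10: "Irradiated study components will be allowed if, after enrollment, a patient develops a condition (e.g., lymphoma) requiring irradiated components". Such a patient stays on blinded components of the assigned type, with irradiation permitted.
- **Unit age.** Section 5.1.3: "No units will be more than 14 days in age". Within that limit the oldest unit is issued first.
- **The hazard.** Section 1 places TA-GvHD risk in immunocompromised recipients of viable donor lymphocytes, which it explains as "non-irradiated blood stored at 4°C less than 2 weeks". It adds that "TA-GvHD has been described in individuals with bone marrow transplants, congenital immune deficiency states, and in some cancer patients", and that "The American Association of Blood Banks recommends irradiation of all blood transfused to individuals with these underlying diseases".
- **Eligibility.** Section 3.2 has eight exclusions. The one concerning the treating physician's view of the product, 3.2.8, applies where the "physician objects to in laboratory leukocyte filtration". The general clause, 3.2.6, covers medical conditions that staff believe would interfere with compliance.
- **Adherence to the assigned group.** Section 4.1: "Except as specified in section 5.3, all RBC transfusions required while on-study" should follow the randomized group. Section 5.3 lists four reasons for stopping blinded components, and an irradiation need is not among them.

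**The concern.** The protocol recognises that some patients need irradiated cells and writes a rule for them, but the rule is tied to when the need arises. A patient who develops lymphoma after entry may receive irradiated study units. A patient who arrives with the same disease and the same need falls under the ban in 5.1.7, and no listed criterion keeps that patient out. The protocol thus describes the hazard and the safeguard itself, and leaves one group without the safeguard unless somebody uses discretion.

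What is at stake is the safety of a few individuals and consistent handling across sites. One site may screen such a patient out under 3.2.6, another may enroll and follow 5.1.7, and a third may irradiate and record a deviation.

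**Working it through.** No figure in the protocol bears on this point and no arithmetic applies. The check is a reading of the product rules against the eligibility rules.

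1. **Is irradiation barred by default?** Yes. Section 5.1.7 gives a general ban with a single cross-reference, to 5.1.10. Section 1 also describes the control product as non-irradiated.

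2. **Does the exception reach a condition present at entry?** No. Its trigger is a condition that develops after enrollment.

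3. **Does any criterion name the need?** The nine items in 3.1 cover HIV status, symptomatic anemia, a non-surgical reason, age, CMV evidence, Karnofsky score, expected survival, availability and consent. The eight in 3.2 cover prior transfusion or transplantation, recent immunoglobulin, recently started antiretroviral, immunomodulator or GM-CSF therapy, TTP, dialysis, conditions interfering with compliance, directed donations, and physician objection to filtration. Count naming irradiation, lymphoma or other malignancy: 0 of 9 and 0 of 8.

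4. **Who is left after the existing exclusions?** Section 3.2.1 removes anyone previously transfused and probably removes marrow transplant recipients. Section 3.2.7 removes patients requesting directed donations, and so most recipients of relatives' blood. Of the groups in Section 1, what realistically remains is some never-transfused cancer patients. Section 5.1.10 itself offers lymphoma as an example of a condition needing irradiated components.

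5. **Can such patients be present at entry?** Nothing prevents it. Section 8.3.1 records past AIDS-defining conditions and 8.3.3.2 records chemotherapy in the 30 days around entry; neither is used to exclude. Lymphoma is on the list in 7.5. The 8.3 items may be collected at any time during the entry visit, so they need not be known before randomization. The history review in 8.1.2 does come before randomization, but it is made against the listed criteria.

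6. **What product would they receive?** Units up to 14 days old (5.1.3), against storage under 2 weeks in the Section 1 description of risk. The two windows nearly coincide. Issuing the oldest eligible unit first moves practice towards the upper end, but fresh units remain allowed. In one arm the cells are also not leukoreduced.

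7. **Is there a way out later?** Section 5.3b leads to leukoreduced cells, not irradiated ones. Section 5.3c lets the patient withdraw consent to study components. Section 5.3.2 describes the units used after removal (same age limit, prestorage filtered, study inventory) without mentioning irradiation. An exit exists, but it depends on choice and is not triggered by the irradiation need.

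**The case against.** The strongest reply is that 3.2.6 already deals with this. A patient who needs irradiated cells cannot comply with a protocol that bars them, so staff may exclude on ordinary meaning; 5.2.6 uses compliance in a sense that includes the blood product. On this view 5.1.10 speaks only of later conditions because earlier ones are caught at screening. Whether a condition requires irradiation is a clinical judgment in any case, and a new exclusion line would rest on the same judgment. Much of this stands: 3.2.6 can be read to cover the case, so the sections do not contradict each other. But it is worded around compliance, does not mention product need, and does not prompt anyone to ask the question. An explicit line would not remove judgment, but it would ensure that the judgment is made.

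A reader might infer that 4.1 and 5.3 together lock such a patient into non-irradiated cells. They do not. The groups in 4.1 are defined by leukoreduction, and 5.1.10 shows that an irradiated unit can still follow the assigned group. The restriction comes from 5.1.7 alone. Nor must the patient receive such cells: 3.2.6, refusal by the physician or patient, and 5.3c are all routes out.

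The safety premise is also limited. Section 1 says TA-GvHD had not been reported in AIDS patients, and its list includes only some cancer patients without naming lymphoma. Against that, it adds that cases may go unrecognized, and the existence of 5.1.10 shows that the authors still regarded the need as real.

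**Conclusion.** The gap is real and minor. By default the text gives a later-onset patient a safeguard and withholds it from a patient with the same condition at entry, who is kept out only by discretion.

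The size is unknown. The protocol gives no share of candidates with such a condition and no TA-GvHD rate in this population, so neither a patient count nor a harm rate can be stated. After the narrowing by 3.2.1 and 3.2.7 the number among the planned 640 is probably very small and could be zero.

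A reader might also infer a diluted contrast between arms, because Section 1 says irradiation markedly reduces immune cell function. The documents do not support that here: for these patients 5.1.7 bars irradiation, so following the text dilutes nothing. No analysis, power figure or estimate is affected.

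The conclusion rests on two assumptions: that some never-transfused candidates have a condition their clinicians would regard as requiring irradiated cells, and that staff would not uniformly apply 3.2.6 to them.

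**What to change.** Add to section 3.2: *Current condition requiring irradiated blood components.* Check it in the pre-randomization history review under 8.1.2 and add it to the eligibility questions in the 4.3.2 telephone call. Leave 5.1.10 unchanged for conditions that arise later.

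Exclusion is preferable to extending 5.1.10 to conditions present at entry. Irradiation suppresses the immune effect under study, so widening the exception would admit patients whose first transfusion, on which the viral-load primary endpoint rests, is already altered.

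The cost is a one-line amendment, one more eligibility question, and the loss of a few otherwise eligible patients, a number the protocol does not allow one to quantify.

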5.2 Blinding

- 5.2.1. All investigators, including the clinical coordinator, will be blinded.
- 5.2.2. All patient care personnel and the patient will be blinded.

- 5.2.3. Only the blood bank technical staff will know the study arm. Clinical coordinators will make a phone call to NERI and receive a coded treatment assignment number. The blood bank technical staff will have a list of translations for the coded treatment assignments. See section 4.1.
- 5.2.4. All study components will have a "generic" study component label. Transfer into a study bag will be performed at the time of issue. Records as to leukoreduction of components will be kept at the blood center or transfusion center.
- 5.2.5. Transfusion medicine physicians will remain blinded at the time of investigation of transfusion reactions (see Sections 7.6, 7.7).
- 5.2.6. A designated transfusion coordinator at each center, other than the investigators and clinical coordinator, will review records to ensure protocol compliance.

5.3 Discontinuation of Blinded Study Components.

There are 4 possible reasons for discontinuation of study products:

a. Patients who meet transfusion reaction criteria for leukoreduction

The criteria in Sections 7.6 and 7.7 will guide the transfusion medicine physician in evaluation of transfusion reactions for the purpose of removing a patient from study components and placing him/her on leukocyte reduced blood components. At the time of evaluation of a transfusion reaction, the transfusion medicine physician will remain blinded. If the patient meets criteria as defined in section 7.7. and signs and symptoms are uncontrolled by premedication with antipyretics, antihistamines or meperidine, the transfusion medicine physician may elect to place the patient on all leukocyte reduced components without unblinding of prior components. However, subsequent components will not be blinded. If, despite providing the patient with leukoreduced blood components, reactions persist, the transfusion medicine physician will be unblinded in order to determine if reactions may have been due to leukocyte filters.

b. Patient's M.D. requests leukoreduced components.

This will be reviewed by the transfusion medicine physician and, if felt to be necessary, will be discussed with the Patient's M.D.

c. Withdrawal of consent to receive a study component.

d. Patients retrospectively found to be CMV sero-negative.

- 5.3.1. Once removed from study components and placed on leukoreduced components, data and specimen collection should continue as scheduled in the protocol.
- 5.3.2. All red cell units transfused to these participants will continue to be \leq 14 days old, prestorage filtered, and issued from the study inventory. However it will not be necessary to transfer the unit to a study bag or affix a blinded study label at the time of issue.

Section 6 -- Concomitant Medications

- 6.1. This protocol will not affect routine clinical care or mandate a change in the use of any prophylactic or therapeutic medication (other than protocol specified preparation of blood components and provision of ophthalmologic examinations). However, within the first 2 weeks after the first 2 transfusion episodes (see section 7.1 for definition), enrollees and their care providers are strongly discouraged from adding new antiretrovirals, systemic immunomodulators, systemic corticosteroids, anti-virals or GM-CSF, because of their potential effect on the study's virologic measures.

Agents falling into these categories are:

Antiretrovirals/Systemic Immunomodulators/GM-CSF

ritonavir (Norvir)
nelfinavir (Viracept)
bis-Pom-PMEA
delavirdine mesylate
didanosine (ddI, Videx)
hydroxyurea (Hydrea)
interleukin 2
interferon alpha (Roferon, Wellferon, Intron A)
interferon beta (Betaseron)
interferon gamma (Actimmune)
lamivudine (3TC)
loviride
indinavir (Crixivan)
nevirapine
saquinavir (Invirase)
stavudine (d4T, Zerit)
thalidomide
zalcitabine (ddC, Hivid)
zidovudine (AZT, ZDV, Retrovir)
other antiretrovirals or immunomodulators
GM-CSF

Antivirals

acyclovir (ACV, Zovirax)
CMV monoclonal antibodies
cidofovir (HPMPC)
famciclovir (Famvir)
foscarnet (Foscavir)
ganciclovir (oral, IV, implant) (Cytovene)
valacyclovir (Valtrex)
other antivirals

Systemic Corticosteroids

prednisone
hydrocortisone
dexamethasone
other systemic corticosteroids

- 6.2 Routine use of corticosteroids as premedication for transfusions is strongly discouraged.
- 6.3 The use of accepted prophylaxis for opportunistic infections [e.g., PCP prophylaxis] is encouraged.
- 6.4 Use of erythropoetin (EPO) and G-CSF is allowed.

Section 7 -- Definitions and Endpoints

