Current transfusion practice for HIV-1-positive patients varies widely and is highly controversial.^{5,6} Although theoretical arguments for allowing autologous donations by HIV-1-positive patients (when possible) are compelling,⁴⁶ concerns over possible transfusion error as well as the infectious exposure of blood bank and hospital personnel has led FDA to discourage this practice. Recent studies showing that erythropoietin (EPO) can reduce blood utilization in HIV-1-infected patients are promising.⁴⁷ However, these studies indicate that EPO is most effective in mild anemias and rarely eliminates the need for all allogeneic blood in HIV-1-positive patients; EPO is also expensive. Consequently, transfusion of allogeneic blood components will probably continue to be the major modality for managing HIV-1-associated anemia and thrombocytopenia for the foreseeable future.^{5,6}

Unfortunately, there is currently a lack of consensus on how best to manage allogeneic transfusion support of HIV-1-infected patients. In a recent AABB survey of institutions with large HIV-patient populations, 36% of hospitals routinely use leukoreduced blood for all HIV-positive patients, 28% routinely irradiate all blood, and 20% use CMV-negative blood for all HIV-positive patients irrespective of recipient CMV status. Although there are no known adverse effects from the use of CMV negative blood components, CMV negative donors are limited in number and, depending on the region, vary from 50% to less than 10% of the population³⁸. The use of filters for leukocyte reduction appears to be relatively safe although rare reactions to the filters, characterized by severe hypotension and respiratory distress, have been recorded⁶⁴. The cost of such specialized component support is substantial, and will grow as more HIV-positive patients require transfusion. Clearly, data are needed to guide policy in this area.

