7.2 On Study

Once randomized, all patients will remain "On Study", unless they withdraw voluntarily, are lost-to follow-up, die or the study ends or is terminated early. If patients refuse blood draws or in-person visits but are willing to be followed by telephone, chart review, or contact with their care provider, then they will remain "On study". If a patient discontinues study components (see section 5.3), then they will remain "On study".

7.3. CMV end organ disease; Criteria for diagnosis:

7.3.1 Retinitis - diagnosis by ophthalmologist.

7.3.2 GI - diagnosis by histopathology with compatible clinical symptoms, signs or laboratory findings

7.3.3 CNS - compatible symptoms/signs with positive CMV CSF culture, PCR or other diagnostic tests.

7.3.4 Pulmonary - requires histopathologic confirmation by biopsy or autopsy.

7.3.5 Other involved organ (e.g., skin) - requires histopathologic confirmation or Ag or nucleic acid detection

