Catheter - related Bacteremia	
a) Isolation of the same bacterial pathogen from a blood culture and a catheter tip or exit site culture in a patient with an indwelling or peripheral intravenous catheter and no other alternative site of infection. OR
 
b) Isolation of a common skin contaminant (e.g., diphtheroids, coagulase-negative staphylococci, Bacillus spp., Propionibacterium spp., or micrococci) from two or more blood cultures drawn on separate occasions in a patient with an indwelling or peripheral intravenous catheter and no other alternative site of infection and the presence of one or more systemic symptoms or signs of infection. OR
 
c) Isolation of a common skin contaminant (see above) from a single blood culture in a patient with an indwelling or peripheral intravenous catheter, no alternative site of infection, systemic signs/symptoms and in whom antibacterial therapy is instituted and continued for at least 72 hours with the patient demonstrating a favorable clinical response.

7.6. Reaction to red blood cell transfusions.

Signs or symptoms must occur during, or within 30 minutes following, a transfusion.

7.6.1. Definite Transfusion Reaction consists of a temperature rise $\geq 1\text{ C}^{\circ}$ with no other explanation for fever and/or a history of recent recurrent fevers (no fever within 7 days).

OR

Chills and/or rigors with no other explanation for symptoms.

7.6.2. Possible Transfusion Reaction consists of a temperature rise $\geq 1\text{ C}^{\circ}$ when other explanations for the fever exist,

OR

Chills and/or rigors, when an other explanation for symptoms exists.

7.7. Any of the following are criteria for considering leukoreduction:

1. 2 definite reactions
2. 1 definite and 2 possible reactions
3. 3 possible reactions
4. One or more of the following without other explanation of the symptoms occurring during or within 30 minutes following a transfusion:
 - a. Hypotension as indicated by a 30% drop in systolic blood pressure or a recorded systolic blood pressure of less than 90mm Hg.
 - b. Respiratory distress requiring intubation and/or supplemental O2 not due to volume overload.
 - c. Chest pain of myocardial origin as defined by ECG changes and/or response to nitroglycerin.

7.7.1 The clinical coordinator will review all transfusion reports and those meeting the above criteria will be brought to the attention of the transfusion medicine physician. See section 5.3.a.

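### Section 5.3 item a applies a premedication condition suited to febrile reactions to the single-event criteria in Section 7.7 item 4, and gives no early way to act on a suspected filter reaction

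*Protocol*

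**What the plan says.** Section 7.7 lists four grounds for considering leukoreduction. Items 1 to 3 count definite and possible reactions, which Section 7.6 defines by temperature rise, chills or rigors. Item 4 opens with "One or more of the following without other explanation of the symptoms occurring during or within 30 minutes following a transfusion" and covers hypotension (4a), respiratory distress needing intubation or oxygen (4b) and chest pain of cardiac origin (4c).

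Section 5.3 item a handles all four alike. The patient must meet a 7.7 criterion, and in addition "signs and symptoms are uncontrolled by premedication with antipyretics, antihistamines or meperidine". The physician then "may elect to place the patient on all leukocyte reduced components without unblinding of prior components". Section 5.2.5 confirms the blind: "Transfusion medicine physicians will remain blinded at the time of investigation of transfusion reactions". A filter cause is taken up last: if, on leukoreduced blood, "reactions persist, the transfusion medicine physician will be unblinded in order to determine if reactions may have been due to leukocyte filters".

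Section 1 says of filters that "rare reactions to the filters, characterized by severe hypotension and respiratory distress, have been recorded". Section 5.2.4 adds: "Records as to leukoreduction of components will be kept at the blood center or transfusion center".

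**The concern.** There are two linked difficulties.

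First, the premedication condition makes sense for recurrent fever and chills, where there is time between reactions to try the listed drugs. Item 4 was written so that one grave, unexplained event is enough to raise the question. Making the response to that event depend on failed premedication can hold the patient on the blinded product until a second reaction.

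Second, two of the item 4 signs resemble Section 1's description of a filter reaction, yet the only change of product that item a offers is filtered blood. For a patient already receiving leukoreduced red cells, that changes nothing about the suspected cause. The blinded physician cannot tell this patient from one on non-leukoreduced cells, for whom the switch is a real change. What is at stake is a further reaction in a patient whose first may have required intubation.

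**Working it through.** The plan gives no figure to reproduce and no frequency for these events, so the check is a count of reactions along each pathway.

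**Step 1. Reactions needed to meet Section 7.7.**
- Item 1: 2 definite reactions.
- Item 2: 1 definite + 2 possible = 3.
- Item 3: 3 possible reactions.
- Item 4: 1 event.

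**Step 2. Add the premedication condition, for an item 4 event in either arm.**
- Premedicated at the index transfusion: the condition can be judged at once, so the switch is available after 1 reaction.
- Not premedicated, condition read literally: index event (1) + a reaction despite premedication on blinded product (1) = 2 reactions before a switch under item a.
- Item 4 exempted from the condition: 1 reaction in both cases.

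**Step 3. Reactions on filtered red cells before unblinding, leukoreduced arm (320 of 640 planned).** One further reaction is assumed to count as persistence.
- Premedicated at the index event, or condition not applied: index (1) + one on open leukoreduced blood (1) = at least 2.
- Not premedicated and condition applied literally: index (1) + one despite premedication (1) + one on open leukoreduced blood (1) = at least 3.
- Early disclosure permitted and used: 1.

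**Step 4. Which product does the patient receive next?**

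| Arm | Kept on study product (4.1, 5.1.1) | Switched (5.3.2) |
|---|---|---|
| Leukoreduced | filtered | filtered |
| Non-leukoreduced | not filtered | filtered |

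In the leukoreduced arm both choices give filtered cells. Disclosure shortens the wait for information from at least 2 or 3 reactions to 1, but does not by itself avoid re-exposure. That needs a non-filtered option in Section 5.3. Section 4.1 already exempts what Section 5.3 specifies, so it need not change.

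**The case against.** The case for leaving the text alone has several parts.

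- *A reader might infer that 5.3 item a contradicts 7.7.* It does not. Section 7.7 sets a threshold for considering leukoreduction, and item a adds a further condition before acting. A physician could also take the view that hypotension is not something the listed drugs control, and treat the condition as met. This stands: the clause is a poor fit, not a contradiction.
- *A reader might infer that the physician must give filtered blood, or that filter reactions were overlooked.* Neither holds. The switch is discretionary, a request by the patient's own physician (5.3 item b) is a separate route, and item a expressly provides for unblinding over filters. The dispute is about timing. But discretion does not supply the missing fact, and for a leukoreduced-arm patient both columns in Step 4 lead to filtered cells.
- *The hazard is thinly supported.* Section 1 calls filters relatively safe and cites one personal observation (reference 64). The protocol does not say whether units filtered before storage carry this risk; item a shows only that it was thought possible. This stands and limits the severity.
- *A reader might infer that early unblinding would be confined to a handful of cases.* The documents do not support that. In Section 1, rarity describes filter reactions. Item 4a and 4b are broader: a systolic reading below 90 mm Hg, or supplemental oxygen alone, is enough. No rate is given.
- *The present design protects the blind.* Switched patients from both arms now go to the same open product, so the switch does not reveal the arm. An open product chosen by filtration status could reveal it to staff and patient, not only to one physician. This stands, and is why early disclosure should be narrow and optional.

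**Conclusion.** The point holds as a minor, patient-safety comment. Its firmest part is the premedication condition: read literally, it raises the reactions preceding a switch under item a from 1 to 2 after an item 4 event in a patient not premedicated at the time. This rests on the literal reading, on the patient being transfused again, and on the separate route in 5.3 item b not being used.

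Earlier disclosure of filtration status is a reasonable addition only for severe 4a or 4b events and only with a non-filtered alternative. Its benefit depends on the filter having caused the event and on further transfusion. No probability can be attached to either part.

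A reader might look for an effect on the trial's conclusions. There is none to claim: overall survival, the one-week HIV RNA change and the sample size do not depend on this clause. Section 7.2 keeps these patients in follow-up ("If a patient discontinues study components (see section 5.3), then they will remain" On Study), so they can be analysed as randomized.

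**What to change.** **Main change.** Add one sentence to Section 5.3 item a stating that the premedication condition does not apply to events under 7.7 item 4. Leave items 1 to 3 as they are. The cost is negligible.

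**Additional change.** In 5.2.5 and 5.3 item a, for severe 4a or 4b events only (for example, those needing intubation or treatment for hypotension), permit but do not require the transfusion medicine physician to learn from blood bank records whether the implicated unit was filtered before choosing the next component. If it was, 5.3 item a and 5.3.2 must also allow a non-filtered component, issued under the generic study label where possible. Item 4c stays blinded, since Section 1 does not link chest pain to filters.

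The costs of the additional change are an unknown number of early unblindings, product choice that may depend on arm in those patients, and possible disclosure of the arm to staff and patient if the product is issued openly.
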